In patients with chronic post-stroke aphasia, we will use a within-subjects repeated-measures design, to evaluate the effects of computerized mass practice audiovisual word-picture matching therapy (5 day/week x1 week) preceded by 20 min of anodal tDCS. Functional improvement will be determined by changes in naming accuracy on trained and untrained word lists.

We are aware that naming is one aspect of the language impairment that may occur after stroke. Thus, we will also measure other aspects of language function, so that if naming does not change there will be additional tests of the hypothesis.

SPECIFIC AIM 2: To compare naming performance between intervention groups (tDCS and sham stimulation).

We will use a single-subject cross-over design to compare two tDCS conditions (1mA anodal vs. sham). Treatment sessions will occur for five consecutive days per condition, with one week between conditions (3 weeks total). Functional improvement will be determined by changes in naming accuracy on trained and untrained word lists.

If neuromodulation (tDCS) preceding treatment is effective for promoting robust recovery in naming ability, as it has demonstrated for motor recovery in patients with chronic stroke and hemiplegia, then we expect the improvement in naming accuracy to be greater following anodal tDCS compared with sham tDCS.

These pilot results will support or not the continued investigation of novel non-invasive neuromodulation techniques.

SPECIFIC AIM 3: To compare naming performance between severity groups (high vs. low functioning aphasia as determined by admission Western Aphasia Battery scores (WAB)).

Preliminary Data

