1. ≥ 18 years of age
2. First single focal unilateral left hemisphere lesion with diagnosis verified by brain imaging (MRI or CT scans) that occurred at least 6 months prior
3. Pre-morbidly right handed
4. Pre-morbidly fluent English speaker
5. Cognitive function sufficient to understand the experiments and follow instructions (per interview with Speech Pathologist)
6. A baseline Aphasia Quotient score between 10 to 94 out of 100 points on the Western Aphasia Battery (neither completely without language comprehension/expression nor fully recovered from aphasia).

Exclusion Criteria:

1. Ongoing use of CNS-active medications
2. Ongoing use of psychoactive medications, such as stimulants, antidepressants, and anti-psychotic medications
3. Presence of additional potential tDCS risk factors:
 - Damaged skin at the site of stimulation (i.e., skin with ingrown hairs, acne, razor nicks, wounds that have not healed, recent scar tissue, broken skin, etc.)

- Presence of an electrically, magnetically or mechanically activated implant (including cardiac pacemaker), an intracerebral vascular clip, or any other electrically sensitive support system
 - Metal in any part of the body, including metal injury to the eye (jewelry must be removed during stimulation)
 - A history of medication-resistant epilepsy in the family
 - Past history of seizures or unexplained spells of loss of consciousness during the previous 36 months
4. Pregnancy in women, as determined by self-report

Visit Schedule

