In this pilot study, 24 participants will be accepted from our referral sources in the department of Neurology and Physical Medicine. There will be 2 measurement periods before the training starts, separated by 3-14 days in order to establish baseline word-finding performance on selected trained and untrained word lists. Following the lead-in period, subjects will participate in a cross-over design training period to compare the two tDCS conditions (1mA anodal vs. sham). The training portion of the study will occur over a total of 3 weeks. During that time, subjects will attend five consecutive, 60-minute training sessions under treatment condition one (anodal vs. sham tDCS), followed by a 1 week rest interval, and then another five consecutive sessions of training under treatment condition two. Order of training word lists and tDCS stimulation condition will be counterbalance across participants. Subjects will undergo four additional evaluations throughout the course of the study, two of which will occur immediately after each of the training conditions (discharge), and the other two of which will occur 1 week after each training condition (follow-up). All study procedures will be administered or supervised by the research coordinator or another licensed Speech-Language Pathologist. All visits will be conducted in the clinical robotics and non-invasive brain stimulation suite at the Feinstein.

Lead-in Period

- Week 1, Visit 1 (approximately 60 minutes)
 - Baseline outcome measures
 - Medical screening
 - Consent
- Week 2, Visit 2 (approximately 60 minutes each)
 - Baseline outcome measures

Training Period Phase I

- Week 3, Visit 3-6 (approximately 60 minutes)
 - 20 min of stimulation condition 1 (sham or anodal tDCS) and 20 min of computerized word-picture matching therapy
- Week 3, Visit 7 (approximately 90 minutes)
 - 20 min of stimulation condition 1 (sham or anodal tDCS) and 20 min of computerized word-picture matching therapy
 - Condition 1 discharge outcome measures

Follow Up Testing Phase I

- Week 4, Visit 8 (approximately 60 minutes)
 - Condition 1 follow-up outcome measures

Training Period Phase II

- Week 5, Visit 9-12 (approximately 60 minutes)
 - 20 min of stimulation condition 2 (sham or anodal tDCS) and 20 min of computerized word-picture matching therapy
- Week 5, Visit 13 (approximately 90 minutes)
 - 20 min of stimulation condition 2 (sham or anodal tDCS) and 20 min of computerized word-picture matching therapy

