-Philadelphia Naming Test short form (PNT): The PNT is a valid and reliable measure of changes in expressive naming across time in stroke patients with expressive aphasia. Performance on the PNT short form has been statistically correlated to PNT long form performance for individuals with aphasia (40, 41, 42).

-Connected Speech Sample including the “Cookie Theft” or “Birthday Party” picture descriptions: Connected speech samples are frequently used metrics of changes in rate, fluency, and language formulation in individuals with aphasia. Audio/visual recordings of naturalistic language samples allow for independent quantitative scoring of language function by clinicians (45, 46).

-“Symbol Cancellation” subtest of the Cognitive Linguistic Quick Test (CLQT): is a valid and reliable non-verbal, visual cancellation task. It is frequently used by clinicians in aphasia literature as a non-verbal control task of attention and visual memory (43).

-Western Aphasia Battery Revised (WAB-R): The WAB-R provides an aphasia quotient for type and severity of aphasia, and is commonly used in the aphasia literature. Changes of >5 points are clinically significant (42, 44, 45).

Transcranial Direct Current Stimulation (tDCS) Application:

Patients will sit in a comfortable chair and a plastic band will encircle the skull. An electrode – a flat 5X5cm plate – will be ensheathed in a disposable cotton sponge and held in place by the band. The reference electrode (cathode) covered by the pad will be placed on the right shoulder and another electrode (anode) will be placed over Broca’s area (left posterior inferior frontal gyrus). To locate the optimal cortical region of the left frontal cortex to be stimulated by the anode electrode, tDCS current modeling of each subject’s MRI will be performed.

A 1mA current will be delivered using the surface rubber-carbon electrodes (35cm²) with surrounding saline soaked sponges (0.9% NaCl) by a battery driven, constant current stimulator (maximum output 2mA) (51). Participants will receive stimulation for 20 minutes while seated (prior to language training), with the anode over the left frontal cortex and the cathode on the right shoulder. Sham tDCS: comparable set-up to real tDCS, 30 seconds real current ramping to 1mA at commencement, then after 5 seconds a slow decrease but no current sustained for 20 minutes.

Computerized Anomia Treatment:

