This self-administered computerized anomia treatment was reported on in a previous study, and demonstrated to be helpful in improving naming accuracy of individuals with aphasia (4). Subjects are asked to perform a 20-minute picture-word matching task following receipt of either sham or anodal tDCS.

Randomization

A single-subject cross-over design will be used to compare two tDCS conditions (1mA anodal vs. sham). The order of anodal or sham stimulation will be counterbalanced across participants, and determined using a random number generator.

Blinding

This is a double blind study. The tDCS device will be covered such that the administrator will code each stimulation condition as either switch “up” or switch “down,” but will remain blinded to which code is anodal vs. sham stimulation. In this way, all investigators interacting with patients will remain unaware of stimulation condition. For the sham condition, the stimulation automatically ramps down after 30 seconds because the perceived sensation of tDCS on the skin has been reported to fade after this period (21). Consequently, participants will also stay blinded to stimulation condition.

Statistical Considerations and Data Analysis

SPECIFIC AIM 1: To evaluate whether anodal tDCS preceding aphasia therapy significantly improves picture naming in individuals with post-stroke aphasia.

Methods to address specific aim 1: A Wilcoxon signed-rank test will be used to compare naming accuracy scores pre and post anodal tDCS condition across participants.

SPECIFIC AIM 2: To compare naming performance between intervention conditions (tDCS and sham stimulation).

Methods to address specific aim 2: If neuromodulation preceding treatment is effective for promoting recovery in language impairment, as it is in robotic hemiplegia treatment, we expect the improvement in naming accuracy to be greater following anodal tDCS compared with sham tDCS. This will be examined with a 2x2 repeated measures ANOVA for both treated and untreated items with stimulation type (A-tDCS,S-tDCS) and time (T1, T2) as factors.

SPECIFIC AIM 3: To compare naming performance between severity groups (high vs. low functioning aphasia as determined by admission Western Aphasia Battery scores (WAB)).

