Methods to address specific aim 3: This will be examined with a 2x2 repeated measures ANOVA with change in naming performance in each stimulation condition (change in naming performance A-tDCS vs. S-tDCS) and severity level (high vs. low functioning aphasia).

Protection of Human Subjects

RISKS TO SUBJECTS

Human Subject Involvement and Characteristics: We anticipate enrolling 12 human subjects. Inclusion and exclusion criteria are stated above in the Research Design and Methods section.

Sources of Material: Sources of research material will be the hospital records providing demographic and medical information including CT or MRI imaging studies, and clinical examinations performed at outpatient facilities run by the Department of Physical Medicine and Rehabilitation of the North Shore University Hospital (NSUH) and LIJ Medical Center (LIJMC), or copies of medical records from outside hospitals provided by participants.

Potential Risks:

tDCS Risks: tDCS is a safe technique that poses a non-significant risk to participants. The safety of this technique has been addressed and tested by multiple researchers (16, 18, 20, 33-34) who have concluded that tDCS, as applied in a manner similar to our proposed protocol has no long-term negative side effects. More than 30 research studies involving hundreds of participants have been published using tDCS. Hundreds more participants have undergone tDCS for unpublished pilot research. No undesirable or long-lasting effects have been reported, nor have any participants reportedly abandoned a study due to discomfort.

Researchers at the National Institute of Neurological Disorders and Stroke (NINDS) conducted a safety study on tDCS, investigating 20-minute sessions of 1 mA and 2 mA current stimulation with healthy controls (n=103) (20). No negative effects were identified. Nitsche and colleagues (2004) found no measurable structural changes in brain tissue due to tDCS (23). Additionally, studies have shown that tDCS can be used safely in stroke patients (11, 18, 34-37). Thus, a growing body of research from different laboratories has shown that tDCS is a safe, non-invasive and painless technique for modulating neural excitability, with measurable but only transient effects. The protocol described here uses stimulation levels that fall well within safety limits established by basic research investigating neural tissue damage, as well as

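### Aim 3 splits the admission WAB score into high and low at a cut the plan never states; testing the Aphasia Quotient as a number would use more of the data and leave no cut to choose

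*Combined protocol and SAP*

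**What the plan says.** Aim 3 appears in Specific Aims and again in Statistical Considerations and Data Analysis. Its purpose is "To compare naming performance between severity groups", defined as "high vs. low functioning aphasia as determined by admission Western Aphasia Battery scores (WAB". The method is a 2x2 repeated measures ANOVA whose factors are "change in naming performance A-tDCS vs. S-tDCS) and severity level (high vs. low functioning aphasia".

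The severity measure is already a number. Inclusion criterion 6 requires "A baseline Aphasia Quotient score between 10 to 94 out of 100 points on the Western Aphasia Battery", and Clinical Outcome Measures states that "The WAB-R provides an aphasia quotient for type and severity of aphasia". The only other WAB figure in the document is the change of more than 5 points described there as clinically significant. Neither the eligibility range nor that change threshold divides high from low, and no median rule or severity band is given.

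Under Blinding, the person giving stimulation "will remain blinded to which code is anodal vs. sham stimulation". The sample size is stated twice: "In this pilot study, 24 participants will be accepted from our referral sources" (Visit Schedule) and "We anticipate enrolling 12 human subjects" (Protection of Human Subjects). That conflict needs its own reconciliation; the present point holds at either size.

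**The concern.** Two things follow from an unstated two-level split.

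First, the ANOVA cannot be run until someone picks a cut, and nothing requires that to happen before naming results are known. A severity result could then arise from the choice of cut alone. Blinding does not prevent this. The severity main effect averages naming change over both conditions and so needs no treatment codes. If the switch code means the same for every participant, exchanging the two labels only reverses the sign of the anodal-minus-sham difference, which leaves the two-sided interaction p-value unchanged.

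Second, even a cut fixed in advance treats everyone on one side as equally severe. If naming change rises or falls steadily with AQ, that makes the relation harder to detect, in a study of 24 or 12 people.

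At stake is how Aim 3 is read. The Specific Aims say that the pilot's results will inform whether this line of work continues, so a severity pattern produced by the cut, or missed because of it, could misdirect a later study.

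**Working it through.** The document gives no alpha, effect size, standard deviation or sample-size derivation, so there is no stated figure to reproduce. The consequences were simulated.

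**Inputs.** From the document: n = 24 or 12; AQ 10 to 94; two severity groups. Assumed: two-sided 5% level; normally distributed change scores; AQ uniform or normal in shape; the sets of candidate cuts; the correlation r between AQ and the change score.

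**Reducing the ANOVA.** Let A and S be a participant's naming change under anodal and sham stimulation, m = (A + S)/2 and d = A − S. The severity main effect is a two-sample t test on m, and the stimulation-by-severity interaction is a two-sample t test on d:

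t = (mean_high − mean_low) / [s_p √(1/n_high + 1/n_low)], with n − 2 degrees of freedom.

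The numeric version is t = r √[(n − 2)/(1 − r²)], also with n − 2 degrees of freedom. Swapping the labels turns d into −d and leaves m alone, so both two-sided p-values stay the same. In 2,000 simulated data sets the largest difference was 0.

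**False positives if the cut is chosen after seeing the data** (no true effect, any significant cut declared, 100,000 trials per case):

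| Candidate cuts | n = 24 | n = 12 |
|---|---|---|
| One cut fixed in advance (median) | 5.0% | 5.0% |
| Three adjacent cuts at the median | 8.6% | 10.2% |
| Lower third, median, upper third | 11.5% | 12.1% |
| 9 cuts, at least 8 per group | 16.9% | – |
| 13 cuts, at least 6 per group | 22.2% | – |
| 7 cuts, at least 3 per group | – | 19.9% |

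The n = 12 entry in the first row comes from a second simulation of 200,000 trials per setting. For the last four rows, where it overlaps, that simulation gave 11.6%, 16.7% and 22.1% (n = 24) and 12.1% and 19.9% (n = 12). It gave 5.0% for the numeric AQ test at both sizes. A wider search raises the rate further: 19 cuts with at least 3 per group at n = 24 gave 31.5%.

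**Information lost by a median split, if the relation is linear.** The share kept is the squared correlation between the score and its split, (E|X|/SD)² for a centred symmetric score.
- Normal: 2/π = 0.637, so 36% is lost.
- Uniform on (−1, 1): (0.5 ÷ 1/√3)² = 0.75, so 25% is lost.

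**Illustrative power under linearity, numeric AQ versus median split** (normal AQ; uniform AQ). The value r = 0.54 was picked because it puts numeric power near 80% at n = 24.

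| | r = 0.54 | r = 0.3 |
|---|---|---|
| n = 24 | 80.8 v 57.7%; 82.2 v 65.5% | 29.9 v 20.0%; 30.3 v 22.8% |
| n = 12 | 46.9 v 28.2%; 47.9 v 32.7% | 15.8 v 11.1%; 15.8 v 12.2% |

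**Other shapes** (uniform AQ, n = 24, r = 0.54), numeric versus median split:
- Smooth S-shape: 80% v 72%.
- Step at the lower third, split at the median: 62% v 48%.
- Step exactly at the cut used: 68% v 85%.
- Peak at mid-range (AQ 52): 7-8% for both.

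**The case against.** The strongest reply is that one sentence stating a cut closes the open-cut problem completely, so replacing the analysis is a preference. The first half stands: a cut fixed in advance holds the error rate at 5%. But it leaves the loss of information untouched. Numeric AQ did better for the linear, S-shaped and off-cut step relations, and worse, among the shapes tried, only for a step at the cut itself. That last loss (68% v 85%) is about as large as the gain under linearity, and the document does not say which shape to expect.

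A reader might infer that numeric AQ removes all freedom of analysis. It does not. If the team looked for curvature and reported whichever of a linear or a centred quadratic term was significant, the false-positive rate would be 9.6% (n = 24) or 9.5% (n = 12), about what three adjacent cuts give. The linear test must therefore be the only test, named in advance.

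Floor and ceiling effects in naming are plausible, though the document does not discuss them. If spread shrinks at both ends of the AQ range (standard deviation proportional to √[p(1 − p)], p = AQ/100, assumed), the ordinary linear test becomes conservative, with a null rate of about 2.7 to 3.1%. This stands and bears on the choice of inference.

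A slope is also not literally a comparison of groups. Model estimates at a stated low and high AQ answer the same question, and the group table can remain beside them.

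Finally, which WAB is the admission one is a matter of reading. The Schedule Chart places outcome measures, which include the WAB-R, at Visits 1 and 2. Visit 1 is the natural reading because eligibility is checked there, but the plan does not say so. Taking the WAB score to mean the AQ is likewise a reading, though the AQ is the only WAB summary score named.

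**Conclusion.** The point holds. Aim 3 reduces a numeric score to two levels at an unstated cut. If a cut were chosen after naming data were seen, each Aim 3 test would carry a false-positive rate of about 9-22% at n = 24 or 10-20% at n = 12, instead of 5%. These figures rest on the assumed level and cut sets. With a median split and a linear relation, 25-36% of the information is lost. The power figures are illustrative only.

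A reader might infer that the cut will be searched, or that the Principal Investigator's four-monthly review gives occasion for it. The document does not support that. Data and Safety Monitoring describes a review of aggregate data for integrity and safety and does not mention naming by severity. The rates above are conditional on a search.

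Nor does the point reach the anodal-versus-sham comparison: Aims 1 and 2 do not use the severity split. This is a low-to-moderate priority improvement to the third aim of a pilot.

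**What to change.** In Statistical Considerations and Data Analysis, Specific Aim 3:

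- Enter admission AQ as a continuous linear covariate in the repeated-measures analysis, with its main effect and the stimulation-by-AQ interaction, as the single pre-stated analysis.
- State which baseline visit supplies the AQ.
- Write down now one low and one high AQ at which model estimates will be reported.
- Provide in advance for heteroscedasticity-robust or permutation inference in case spread differs across AQ.
- Treat any look at curvature as descriptive, with no effect on the test.
- Keep high versus low as a supporting table or sensitivity analysis, with its numeric cut written into the plan before naming data are examined by severity. Fixing it merely before unblinding is too late, for the reasons given on blinding.

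If the team prefers to keep the 2x2 ANOVA, stating the cut and the visit now is the minimum repair. It closes the open-cut problem but not the loss of information.

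The cost is plan wording only, because AQ is already needed for eligibility. The price is an assumed linear form: the numeric test would do worse than the split if the truth is a step at the cut used, and neither analysis detects a mid-range peak well.

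### The protocol gives two planned sample sizes, 24 and 12, and nothing in it reconciles them

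*Combined protocol and SAP*

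**What the plan says.** The planned size appears twice in the combined protocol and SAP.

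- Under Research Design and Methods, Visit Schedule: "In this pilot study, 24 participants will be accepted from our referral sources". The same paragraph describes the lead-in measurements and then says that "subjects will participate in a cross-over design training period to compare the two tDCS conditions".
- Under Protection of Human Subjects, Human Subject Involvement and Characteristics, which opens the part on risks: "We anticipate enrolling 12 human subjects".

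Other parts bear on whether the figures can be reconciled, but none gives a number of participants. The Randomization section says "The order of anodal or sham stimulation will be counterbalanced across participants, and determined using a random number generator", with no number per order. The Schedule Chart labels Visits 1 and 2 as screens and puts informed consent at Visit 1. Recruitment and Informed Consent ties joining the study to signing the consent form, and allows withdrawal at any time without stating an expected rate. Statistical Considerations and Data Analysis names the tests for the three aims but states no sample size, significance level, power, standard deviation or dropout.

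**The concern.** One document cannot plan for both 24 and 12 people unless the two figures count different things, and the text does not say that they do. Three matters depend on the answer.

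- **Precision.** Aim 2 is a within-subject contrast, so its precision depends directly on the number of participants.
- **The human-subjects declaration.** If 24 is intended, the section on risks states half the people to be enrolled. If 12 is intended, the Visit Schedule sets a recruitment target of twice the declared number.
- **The end of recruitment.** With no sample-size rationale elsewhere, recruitment could end at 12 or at 24 and either could be reported as planned.

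**Working it through.** **Inputs from the document.** N = 24 (Visit Schedule) and N = 12 (Human Subject Involvement and Characteristics). Every participant receives both conditions. Neither figure can be re-derived, because the document gives no effect size, standard deviation, significance level, power or dropout rate.

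**Step 1: can the two figures be linked?**

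- *24 screened, 12 enrolled.* The Visit Schedule does not describe the 24 as people screened; it carries its participants into training. Consent is at Visit 1, and the consent section treats signing as joining the study. Anyone lost at the screening visits after consent has therefore already enrolled, so such losses cannot turn 24 into 12 enrolled. The 24 could still count referrals before consent, but the Visit Schedule does not say so.
- *12 per treatment order, 24 in total.* The arithmetic fits (2 × 12 = 24), but the human-subjects section gives 12 with no such qualifier.
- *24 before dropout, 12 after.* This needs a loss of 1 − 12/24 = 50%. No dropout allowance is stated, and the 12 are described as enrolling, not completing.
- *Counterbalancing.* The Visit Schedule says "Order of training word lists and tDCS stimulation condition will be counterbalance across participants". If stimulation order and word list are fully crossed (an assumption), there are 2 × 2 = 4 combinations. Then 24/4 = 6 and 12/4 = 3, both whole numbers, so neither figure is excluded.

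No reading is supported by the text.

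**Step 2: what the difference means for Aim 2.** The planned analysis is a "2x2 repeated measures ANOVA for both treated and untreated items with stimulation type" and time as factors. With both factors within subject, the stimulation-by-time interaction is equivalent to a paired t-test on the difference between the two changes. The half-width of the confidence interval, in units of the standard deviation of that paired difference, is

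half-width = t(0.975, n − 1) / √n

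- n = 24: 2.069 / √24 = 0.422
- n = 12: 2.201 / √12 = 0.635
- ratio: 0.635 / 0.422 = 1.50

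The ratio is the product of the standard-error ratio, √(24/12) = 1.414, and the ratio of t critical values, 2.201/2.069 = 1.064. The standard deviation cancels if it is the same at either size.

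**Step 3: sensitivity.** The document sets none of the conditions below; they are assumptions.

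| Assumption | Larger n | Smaller n | Ratio |
|---|---|---|---|
| 95% CI, 24 vs 12 | 0.422 | 0.635 | 1.50 |
| 90% CI, 24 vs 12 | 0.350 | 0.518 | 1.48 |
| 97.5% CI, 24 vs 12 | 0.489 | 0.749 | 1.53 |
| 95% CI, one degree of freedom used for a period term | 0.423 | 0.643 | 1.52 |
| 95% CI, 20 vs 10 completers | 0.468 | 0.715 | 1.53 |
| 95% CI, 18 vs 9 completers | 0.497 | 0.769 | 1.55 |

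The ratio stays between 1.48 and 1.55.

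**Step 4: Aim 3.** This aim compares high and low severity. With an equal split (an assumption), the groups would be 24/2 = 12 each or 12/2 = 6 each.

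**The case against.** The strongest reply is that the two figures may count different things, in which case neither is wrong and only a definition is missing. The Visit Schedule speaks of accepting people from referral sources, the Schedule Chart calls the first two visits screens, and the exclusion criteria are broad. This cannot be ruled out for referrals counted before consent. But no sentence says it, and the Visit Schedule goes on to describe training. What stands is that one figure may be undefined rather than wrong, and the fix allows for that.

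It can also be said that 24 is the more operational figure: it sits in the design section and is stated firmly, while the 12 is only anticipated. That is a fair reason to lean towards 24, but the text does not settle it.

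A third reply is that the precision ratio is generic. Halving any paired design of this size gives about 1.5; the trial is a pilot, and the plan sets no confidence interval or precision target. This is correct. The ratio shows only that the choice of number matters. The factor of 2 is the only magnitude the document itself supplies.

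Finally, no planned test becomes invalid at either number, and the document states no approval consequence of changing the declared 12. Both points are accepted. They do not remove the contradiction, because the planned number of participants is a basic design figure that recruitment and the human-subjects declaration rely on.

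**Conclusion.** The concern holds. The document states 24 and 12 as the planned size, in current text, with nothing to reconcile them. This is an inconsistency between two stated counts, not a miscalculation. The figures differ by a factor of 2. If 24 is intended, the human-subjects section declares 12 of 24, or 50%.

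The 95% confidence interval for the Aim 2 contrast would be about 1.50 times as wide at 12 as at 24 (1.48 to 1.55 across the variants tried). That rests on treating the interaction as a paired t-test and on the same standard deviation of the paired difference at either size. No absolute precision, power or detectable effect is claimed, because the document gives no inputs for one. Nor is any view taken on which figure is right. The point must be corrected, since the protocol as written does not determine its own sample size.

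**What to change.** State one planned number in both the Visit Schedule and Human Subject Involvement and Characteristics, say whether it counts participants consented, randomised or completing, and use it as the recruitment target. If the two figures are meant to count different things, define each and give the link, for example an expected screening loss or a number per treatment order. A precision statement would be useful but is not needed to resolve the contradiction.

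The cost is a text correction in at least one section. If 12 is intended, the Visit Schedule changes and the attainable precision is the less favourable of the two. If 24 is intended, the number declared in the human-subjects section doubles from 12 to 24, which is a change of substance to that declaration.
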